**Project Title: Exploration of responses to compassion in a clinical population**

**NCT number: TBC**

**Date: 20th March 2018**

### **Project executive summary**

This project focuses on exploring responses to compassionate imagery, a technique from Compassion Focused Therapy (CFT; Gilbert, 2014). Evidence has documented that CFT decreases depression, shame, self-criticism and increases self-esteem (Kirby, 2016). Compassion-focused imagery (CFI) is a key technique in CFT, which involves visualizing compassion towards others, or imagining people, places or objects directing compassion towards oneself. Single trials of CFI have shown a reduction of negative affect and physiological changes associated with the attenuation of threat-focused behaviors (e.g. Rockliff et al., 2008). Regular CFI practice has increased self-compassion and reduced negative affect in both clinical and non-clinical populations (Gilbert & Irons, 2004; McEwan & Gilbert, 2016). Unfortunately, CFI can create threat-focused responses in some individuals. However, these findings have been based on tasks involving receiving compassion from others.

The present study therefore aimed to explore participants' responses to imagery exercises involving self-compassion, in comparison to a relaxation task (to control for certain task demands but without the compassion element), and a control task ( reading a magazine).

### **GENERAL OBJECTIVE**

To explore responses to self-compassionate imagery in comparison to relaxation and a control task, in a clinical population.

### **SPECIFIC OBJECTIVES**

1. How do clinical participants initially respond to *self*-compassionate imagery in an initial trial, compared to relaxation and a control task? (using self-report and HRV measures)
2. Do any threat responses reduce following repeated trials of self-compassionate imagery?

### **METHODS**

### Participants and process of recruitment:

We plan to recruit a sample of 25 participants for this study, based upon other studies of compassionate imagery with similar designs (Rockliff et al., 2008; Duarte et al., 2015).

Inclusion criteria are:

1. Clinical level of anxiety or depression (defined for this study  $\geq 8$  on the OASIS or ODSIS)
2. High self-criticism (we selected a cut-off of 0.5 standard deviations above the mean in self-inadequacy or self-hatred on the FSCRS). Based upon a validation in Colombia of the FSCRS by Naismith, Duran Ferro, Ingram, & Jiménez Leal (Submitted), this represents  $\geq 24$  in self-inadequacy or  $\geq 8$  in self-hatred.

These criteria were selected because these interventions are designed to help a clinical population presenting with high self-criticism. Offering this to a non-clinical population (i) reduces the likelihood of observing significant changes, and (ii) will not allow us to help those who present with higher needs.

Nonetheless, those who complete the initial screening and do not meet inclusion criteria will be invited to a group session to learn compassion techniques. They will also receive compassion materials via email at the end of the study.

For recruitment, posters will be hung inside the campus of the University of the Andes. The same information will be published in university social media pages.

### Design:

Participants will be randomized to complete 3 or 4 trials (see details below) using a 2:1 ratio, using a randomization sequence drawn up prior to the study start. This will allow us to explore in a small subgroup whether a fourth trial impacts results. We are also running a related study, which will explore the effects of psychotherapy that will be offered following these 3-4 trials, and we anticipate that a fourth trial will increase probability of dropout from the second study, therefore we will not assign all participants to do the fourth trial.

### Measures:

See Appendix 2 for copies of the questionnaires that we intend to use that are not validated.

- 1. Demographics**
- 2. Self-report form – Physiological variation**
- 3. Overall Depression Severity and Impairment Scale (ODSIS)**
- 4. Overall Anxiety Severity and Impairment Scale (OASIS)**
- 5. Forms of Self-Criticism/Attacking and Self-Reassuring Scale (FSCRS)**
- 6. Positive and negative affect generated**

**7. Heart Rate Variability (HRV).** Heart rate variability (HRV) is a physiological measure that allows us to quantify small changes in anxiety moment by moment, that a questionnaire cannot quantify. In this study it will allow us to measure whether participants respond to compassion with a threat-based response or a relaxed response (we expect that after 3-4 trials, all participants will respond with relaxation or a neutral response, but we predict that at the start, some will respond with threat-based responses).

We will use the BioPac system to collect HRV data. Electrodes will be placed using the Lund guidance which is considered the most stable, least invasive, and with high diagnostic accuracy. Using the program Acqknowledge, we will analyse beats per minute (BPM) and ratios of sympathetic and parasympathetic activity. Specifically, we will use the Root Mean Square of the Successive Differences (RMSSD) of RR intervals (Task Force of the European Society of Cardiology and the North American Society of Pacing and Electrophysiology, 1996). RMSSD was selected because there is no agreed clinically-significant change value for analysing HF HRV data (see Data analysis section).

#### Procedure

Participants will complete an initial screening questionnaire online including: an informed consent (see Appendix 1), demographics questions, ODSIS, OASIS and FSCRS. Eligible participants will be invited to attend in-person sessions. In each session, HRV will be measured by a research assistant whilst the participant engages in three 4-minute tasks in the following order:

- **Control task:** participants will read a magazine with neutral content for 4 minutes
- **Relaxation imagery** (see appendix 3): participants will complete a relaxation exercise of beach or forest imagery for 4 minutes.
- **Compassion-focused imagery:** participants will complete a compassion-focused imagery for 4 minutes (see appendix 3).

#### **Data analysis**

Paired *t*-tests will be run (i) to estimate differences in HRV during the self-compassion imagery, relaxation imagery and the control task, (ii) to examine changes in self-reported positive and negative affect from pre-CFI to post-CFI, (iii) to explore whether changes in positive and negative affect during CFI are greater or smaller from Trial 1 to Trial 3.

To complement group-level analyses, we will use reliable and clinically-significant change analyses. We will firstly report how many participants show a reliable change (Jacobson & Truax, 1991) in positive or negative affect following CFI.

We will also calculate how many individuals show a clinically-significant HRV response ( $\geq 5$ ms change in RMSSD within one individual between two different tasks).

Finally, we will report the number of positive and negative clinically-significant responses for both relaxation and compassion in each trial, in order to (i) compare effects of compassion versus relaxation at trial 1, and (ii) explore whether repeated trials improved response to each task.

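### Objective 1 asks for a self-report comparison of compassion-focused imagery with relaxation and control, but the only clearly planned between-task analysis is for HRV

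*Combined protocol and SAP*

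**What the plan says.** **Objective 1 (Specific Objectives).** It concerns the response to CFI at an initial trial, "compared to relaxation and a control task? (using self-report and HRV measures". It therefore has three elements: a time point, two comparator tasks and two kinds of measure.

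**Purpose of the relaxation task (Project executive summary).** It is included "to control for certain task demands but without the compassion element".

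**Planned analyses (Data analysis).**
- Test (i): "to estimate differences in HRV during the self-compassion imagery, relaxation imagery and the control task".
- Test (ii): "to examine changes in self-reported positive and negative affect from pre-CFI to post-CFI".
- Test (iii): whether affect change during CFI differs between Trial 1 and Trial 3.
- Reliable-change count: participants with a reliable change "in positive or negative affect following CFI".
- HRV count: participants with "a clinically-significant HRV response", set at 5 ms or more in RMSSD between two tasks in the same person.
- Closing count: "the number of positive and negative clinically-significant responses for both relaxation and compassion in each trial", intended among other things to "compare effects of compassion versus relaxation at trial 1".

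**Session (Procedure).** The tasks run in a fixed order: control, relaxation, CFI. HRV is recorded throughout. The supplied text does not say when affect is rated.

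**The concern.** Self-report is one of the two kinds of measure named in Objective 1, yet each analysis that clearly concerns affect looks at CFI alone. A change from before to after CFI shows that affect moved around that task. It does not show whether compassion moved it, or whether guided imagery of any kind, a few quiet minutes or the wish to comply would have done the same. The relaxation task was built into the design to help make that distinction, and the affect analysis does not use it.

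The study could then report a significant affect change after CFI, or a number of reliable changers, as its self-report answer to a comparative question that was never analysed.

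A smaller, related point is that tests (i) and (ii) and the reliable-change count name no trial, whereas Objective 1 is about the initial one.

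**Working it through.** **Step 1. Objective against analyses**

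| Analysis | Measure | Compares tasks? | Trial named? |
|---|---|---|---|
| Test (i) | HRV | Yes, all three | No |
| Test (ii) | Affect | No, CFI only | No |
| Test (iii) | Affect | No, CFI only (between trials) | Trials 1 and 3 |
| Reliable-change count | Affect | No, CFI only | No |
| RMSSD count | HRV | Yes, any two tasks | No |
| Closing count | Clinically significant responses | Compassion versus relaxation | Each trial, including Trial 1 |

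Only the closing count could carry a between-task affect comparison. The term it counts has a threshold for RMSSD alone, and the Measures section ties the choice of RMSSD to the availability of a clinically significant change value. Affect is given a different criterion, reliable change, and only after CFI. The natural reading is that the closing count is an HRV count.

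**Step 2. What test (ii) can show**

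The plan gives no power calculation to reproduce; 25 is taken from similar studies. Inputs: n = 25 (planned recruitment; complete data assumed) and two-sided 0.05 (assumed). The affect SD and correlations are not given, so effects are in units of the SD of a change score.

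Non-central t with 24 df and non-centrality d√25, critical value 2.064:
- d = 0.3: significant in 0.302 of studies.
- d = 0.5: significant in 0.670 of studies.

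If that change is non-specific, test (ii) detects it just as often as it would a compassion effect.

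**Step 3. What a between-task contrast adds**

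Let Y0 be the rating at session start and Y1, Y2, Y3 the ratings after control, relaxation and CFI. CFI change minus relaxation change is (Y3 − Y2) − (Y2 − Y1) = Y3 − 2·Y2 + Y1. CFI change minus control change is (Y3 − Y2) − (Y1 − Y0).

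With equal change-score SDs and correlation r between them, the SD of the contrast is √(2(1 − r)) times the change-score SD. Independent rating errors alone would give r = −0.5 for the first contrast, because Y2 is shared, and r = 0 for the second. The actual r is unknown.

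For a single paired change at n = 25, the effect detectable at 80% power (assumed) is 0.584 SD and the 95% CI half-width is 2.064/√25 = 0.413 SD. At the Bonferroni level 0.05/4 = 0.0125, the detectable effect is 0.715 SD. Multiplying by the SD ratio:

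| r | SD ratio | Detectable, 0.05 | 95% CI half-width | Detectable, 0.0125 |
|---|---|---|---|---|
| −0.5 | 1.732 | 1.01 | 0.71 | 1.24 |
| 0 | 1.414 | 0.83 | 0.58 | 1.01 |
| +0.5 | 1.000 | 0.58 | 0.41 | 0.71 |

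Two affect scales times two comparators is four contrasts. Tested unadjusted, the familywise error is 1 − 0.95⁴ = 0.185 if they are independent.

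**Step 4. How far the contrast protects**

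- If the non-specific change is equal in all tasks, it cancels, and the contrast is significant in 5% of studies whatever r is.
- If a change of 0.3 to 0.5 SD occurs only in the last task, for reasons unrelated to compassion, the contrast is significant in 13% to 28% of studies at r = −0.5, 17% to 40% at r = 0, and 30% to 67% at r = +0.5. The lower rates reflect a noisier contrast, not better attribution.
- If relaxation has already pushed affect towards a floor or ceiling, Y3 − Y2 has little room and the contrast is biased against CFI.

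**The case against.** The strongest reply concerns the closing count. The plan introduces reliable and clinically significant change together, and the paper it cites for reliable change has clinical significance in its title. The count at Trial 1 could therefore be meant to include affect. That reading is possible but weaker, for the reasons in Step 1. It shows that the wording needs settling; it does not supply a stated affect comparison.

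A reader might infer that the closing count leaves out the control task altogether. The documents do not support this. An HRV response is defined between two different tasks, so a response to relaxation or to compassion needs a reference, and control, which runs first, may be the unstated one.

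A reader might also infer that the missing trial label is a fault of the affect analyses in particular. It is not: test (i) for HRV names no trial either, and test (iii) already requires each participant's Trial 1 CFI affect change.

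Nor does the text show that affect is not rated around relaxation and control. Rating times are not in the supplied text and the questionnaire appendix was not available. If those ratings exist, the data are there, but the analysis plan still names no use for them.

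Two further objections stand in part. The study is exploratory and names no primary or confirmatory affect endpoint, which limits the seriousness of the point but does not give the stated question an analysis. And because CFI is always last, a between-task contrast only partly cures the attribution problem.

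**Conclusion.** The mismatch holds on the text alone. Objective 1 promises a between-task comparison by self-report, and no listed analysis clearly provides it. It should be fixed before analysis. It does not affect the HRV comparison or test (iii), since Objective 2 names no comparator.

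The 30% to 67% figure should not be taken as a false-positive rate. It is ordinary power for a real but non-specific change, and the problem is what that change would be attributed to. It rests on assumed effects of 0.3 to 0.5 SD, an assumed 0.05 level and 25 complete participants.

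Nor should the added contrasts be taken to isolate compassion. They remove what the tasks share equally. They do not remove order, carry-over or end-of-session effects, and at this sample size they detect only effects of about 0.58 to 1.01 change-score SD, depending on an unknown correlation.

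**What to change.** 1. State when affect is rated and what counts as pre-CFI (immediately before CFI, or session start). If affect is rated around each task, add for Trial 1, on each affect scale, CFI change minus relaxation change and CFI change minus control change, as paired differences with 95% CIs. Report reliable-change counts for all three tasks.
2. State that tests (i) and (ii) and the reliable-change count are reported for Trial 1 when answering Objective 1, and label test (ii) as uncontrolled. Say whether the closing count covers HRV only, and which task is its reference.
3. State that CFI always comes last, so order, carry-over (including a floor or ceiling effect that could work against CFI) and end-of-session effects remain, and carry this into the conclusions.
4. If affect is rated only around CFI, limit the Objective 1 between-task comparison to HRV and report affect change as uncontrolled.

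Test (iii) stays as it is.

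**Cost.** If the ratings exist, this is a change of wording. If they do not, the choice is between short extra ratings and item 4, which takes one sentence. The statistical cost is limited precision and four added comparisons (Step 3), so the contrasts should be presented as exploratory estimates with CIs, with the multiplicity disclosed.

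### CFI always follows relaxation directly, and affect is analysed only as pre-CFI to post-CFI change, so the affect results mix the CFI response with relaxation carry-over

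*Combined protocol and SAP*

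**What the plan says.** The Procedure section has each participant complete "three 4-minute tasks in the following order": magazine reading, then relaxation, then CFI. In the task just before CFI, "participants will complete a relaxation exercise of beach or forest imagery for 4 minutes". No counterbalancing or washout is stated. The randomisation in the Design section is to three or four trials and does not vary task order.

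In the Data analysis section, affect enters in three places:

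- Test (ii) is a paired t-test "to examine changes in self-reported positive and negative affect from pre-CFI to post-CFI".
- Test (iii) asks whether that change differs between Trial 1 and Trial 3.
- An individual-level count gives "how many participants show a reliable change (Jacobson & Truax, 1991) in positive or negative affect following CFI".

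All three concern CFI only. The later count covering both relaxation and compassion ("we will report the number of positive and negative clinically-significant responses for both relaxation and compassion in each trial") follows the RMSSD rule and is not defined for affect.

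The Measures section lists the instrument as "Positive and negative affect generated". The available text gives no scale range, reliability or time of rating. For the tasks themselves, the Procedure section says only that "HRV will be measured by a research assistant whilst the participant engages in" them.

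**The concern.** Specific objective 1 asks how participants respond to self-compassionate imagery compared with relaxation and a control task, and names self-report as well as HRV. A change score taken only across CFI has no comparator, so it cannot answer the self-report half of that question.

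The fixed order makes this worse, because the preceding task is itself meant to shift affect. An affect change across CFI may be due to CFI, to relaxation fading, or (with a session-start baseline) to relaxation itself. The direction of the bias depends on a rating time that the plan does not state.

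What is at stake is the study's main reading. Specific objective 2 asks whether threat responses diminish with repetition. A rise in negative affect after CFI would naturally be taken as threat and a fall as benefit, and either could come from the relaxation task.

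**Working it through.** **Is there a plan figure to reproduce?** No. The sample size of 25 rests on precedent. The plan gives no alpha, SD, effect size or reliability, so everything below except n = 25 is assumed.

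**Step 1: two readings of the baseline.** Let R be the relaxation effect on affect, C the true CFI effect, and w the part of R that fades during CFI.

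- Rating between relaxation and CFI: observed change = C − w.
- Rating at session start (ignoring any effect of the control task): observed change = R + C − w.

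The observed change equals C only if w = 0 on the first reading, or R = w on the second. The plan collects nothing stated that would show this.

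**Step 2: size of the effect on test (ii).** Assume C = 0, the first reading, n = 25, a two-sided 5% test, w = 0.15 or 0.30 SD, and pre-post correlation ρ of 0.6, 0.7 or 0.8.

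SD of change = √(2(1 − ρ)); noncentrality = 5w / SD of change; df = 24; critical t = 2.064.

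| w (SD) | ρ | SD of change | Noncentrality | P(significant) |
|---|---|---|---|---|
| 0.15 | 0.6 | 0.89 | 0.84 | 0.13 |
| 0.15 | 0.7 | 0.77 | 0.97 | 0.15 |
| 0.15 | 0.8 | 0.63 | 1.19 | 0.21 |
| 0.30 | 0.6 | 0.89 | 1.68 | 0.36 |
| 0.30 | 0.7 | 0.77 | 1.94 | 0.46 |
| 0.30 | 0.8 | 0.63 | 2.37 | 0.62 |

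Fewer than 0.3% of studies are significant in the opposite direction. By symmetry, the same figures apply on the second reading, in favour of CFI, if 0.15 to 0.30 SD of relaxation effect is still present after CFI.

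**Step 3: size of the effect on the reliable-change count.** The Jacobson-Truax threshold is 1.96 × SD × √(2(1 − r)). Assume a 0 to 100 negative-affect scale, SD 20, r = 0.8 and inert CFI. The threshold is 1.96 × 20 × √0.4 = 24.8 points. Over mean scores before relaxation of 30, 50 and 70, simulation gives these expected numbers of reliable worseners out of 25:

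| Relaxation effect | None fades | Half fades | All fades |
|---|---|---|---|
| 10 points | 0.4 to 0.6 | 1.1 to 1.4 | 2.5 to 2.9 |
| 20 points | 0.3 to 0.6 | 2.0 to 3.0 | 7.4 to 8.5 |

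The starting level has little influence, so this does not depend on participants being near the end of the scale.

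**Step 4: is there also a floor or ceiling problem?** With the same scale and r = 0.8, after a 20-point relaxation effect the share lacking room for reliable improvement is 77%, 40% and 10% at starting means of 30, 50 and 70. The share lacking room for reliable worsening is 0%, 1% and 10%. With a mean of 70 and a 10-point effect the asymmetry reverses: 4% cannot improve and 22% cannot worsen. The documents do not say which case applies.

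A cap alone also does not create worsening. With inert CFI and no wear-off, improvers and worseners are equal, at 0.3 to 0.6 of 25 each. What a cap can do is hide benefit. With a true 10-point CFI gain and a mean of 30, expected improvers fall from 2.4 to 1.2 of 25 when relaxation lowers scores by 20 points. At a mean of 70 there is no loss (2.8 against 2.9).

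**The case against.** The strongest reply is that the bias rests on things the documents do not establish: that relaxation shifts affect, that the shift fades within a four-minute task, and that affect is rated between the two tasks. Ratings after every task may already be planned in Appendix 2, which is not in the available text. This stands as a limit on the figures. It does not rescue the analysis, because the Data analysis section still plans no affect contrast except the one across CFI, and both baseline readings leave relaxation in the result.

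A second reply is that a carry-over of constant size cancels in test (iii). That is correct. It fails only if the relaxation effect or its fading changes with practice. The documents do not show such a change, though the plan itself proposes to explore whether repeated trials improve the response to each task.

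A reader might go further and infer that reliable improvement is capped while worsening is free, so that the counts tilt toward harm. The documents do not support this. Scale range, starting level, reliability and rating time are not given. The sample is selected for clinical anxiety or depression and may start well away from the floor of a negative-affect scale, and the full-sample counts stay balanced unless something wears off.

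A reader might also infer that fading relaxation would be scored as an adverse response. The plan attaches no direction label to reliable affect change, and its positive and negative response count is an HRV rule.

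**Conclusion.** The concern holds in a limited form. Because the order is fixed and the only affect contrast is the change across CFI, the affect results cannot separate the response to CFI from relaxation carry-over. They also cannot supply the self-report comparison that objective 1 asks for. This follows from the documents alone, whichever baseline is meant.

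The size is illustrative. The 13% to 62% false-positive rate requires inert CFI, wear-off of 0.15 to 0.30 SD, a correlation of 0.6 to 0.8 and a rating between the two tasks. With no carry-over the rate is the nominal 5%. The direction of bias is also open: against CFI if the baseline follows relaxation, in its favour if the baseline is at session start. A floor or ceiling effect remains a possibility to describe, not a demonstrated flaw. The point merits a change because the remedy is cheap and bears on the study's main question.

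**What to change.** **Procedure section.** State the times of the affect ratings: after the control task (before relaxation), between relaxation and CFI, and after CFI, with the same instrument each time.

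**Data analysis section.**

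- Report post-CFI change from both earlier ratings.
- Report the affect change across relaxation, and compare it with the change across CFI by a paired test.
- Report reliable improvement and reliable worsening separately for each scale, out of the full sample, and state the reliability and SD used for the threshold.
- Give the share of participants without room to change by the threshold in each direction, as description only.

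Two additions should be avoided. The first is restricting each count to participants with room to change. This selects on a noisy baseline, and regression to the mean then favours improvement. Take inert CFI without wear-off, a floor 1.5 SD below and an upper end 2.5 SD above the session-start mean, r = 0.85 and a 0.6 SD relaxation effect. The full-sample rates are 1.7% improved and 1.7% worsened; the restricted rates are 4.0% and 1.7%. The second is counting worsening as a response to CFI only when it also passes the pre-relaxation level. With no matching rule for improvement this is one-sided, and it would reclassify the threat responses that objective 2 is about.

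**Cost.** About a minute more per session, or wording only if these ratings are already planned. Carry-over becomes visible but is not removed, because the order stays fixed; the comparison of relaxation with CFI remains a comparison of a second task with a third. The three ratings allow affect levels to be compared after each task, but a change score for the control task would need a further rating at session start.

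### Objective 2 is about threat responses, but the only across-trial test averages over everyone, and the planned individual counts do not follow the same people from Trial 1 to Trial 3

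*Combined protocol and SAP*

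**What the plan says.** The second of the SPECIFIC OBJECTIVES is: "Do any threat responses reduce following repeated trials of self-compassionate imagery". Under Measures, in the HRV item, the protocol adds "we predict that at the start, some will respond with threat-based responses", and for the later trials "we expect that after 3-4 trials, all participants will respond with relaxation or a neutral response". No number is attached to the word some.

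The Data analysis section opens with "Paired *t*-tests will be run" and lists three uses. The first compares HRV between tasks, the second compares affect before and after the compassion imagery, and the third is "iii) to explore whether changes in positive and negative affect during CFI are greater or smaller from Trial 1 to Trial 3". Only the third compares one trial with another, and it is not restricted to people who showed threat.

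The section then adds individual-level analyses as a complement. For affect: "We will firstly report how many participants show a reliable change". For HRV, a response is a change in RMSSD of at least 5 ms between two tasks. Finally, "we will report the number of positive and negative clinically-significant responses for both relaxation and compassion in each trial", partly to see whether repetition improved the response to each task.

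On size: "We plan to recruit a sample of 25 participants for this study, based upon other studies of compassionate imagery with similar designs". No effect size, SD, alpha or power is given.

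**The concern.** Objective 2 concerns the people who show threat, whereas test (iii) concerns the average person. If only some show threat, the mean change contains their improvement multiplied by their share of the sample, plus whatever happened to the rest.

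The wording of the test also has no direction. For a person whose negative affect rises during the imagery, a smaller change at Trial 3 is an improvement. For a person whose negative affect falls, a smaller change is a weaker benefit. The two can cancel.

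Two misreadings become possible. A null result could be taken as persistence of threat when every threat response had gone. A significant result could be taken as resolution of threat when only the others had changed.

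**Working it through.** **The plan's own figure.** The sample size of 25 rests on precedent and has no inputs, so there is nothing to reproduce. A two-sided paired t-test at 0.05 with n = 25 has 80% power for a mean change of about 0.58 SD of the differences.

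**Inputs.** From the plan: n = 25, a paired t-test, and an expected end state with no threat. Assumed, because the plan is silent: two-sided alpha 0.05, no dropout, k threat responders whose negative-affect response falls by 1 SD (full resolution), and the other 25 − k changing by e, where a positive e means lost benefit. The SD is 1 *within each subgroup*.

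**Formulas.** Group mean change = [k × (−1) + (25 − k) × e] / 25. SD over all 25 differences = √[1 + p(1 − p)(1 + e)²], with p = k/25. Rejection rates come from simulating the paired t-test.

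For k = 6 and e = +0.25:
- Suppose the 6 go from +1.0 to 0 and the other 19 from −0.50 to −0.25.
- Trial 1 mean = (6 × 1.0 − 19 × 0.50)/25 = −0.14.
- Trial 3 mean = (0 − 19 × 0.25)/25 = −0.19.
- Difference = −0.05.
- Overall SD = √[1 + 0.24 × 0.76 × 1.25²] = 1.13.

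| Threat responders, all resolving (k) | Change in the others (e) | Group mean change | Test (iii) significant |
|---|---|---|---|
| 6 | +0.25 (benefit fades) | −0.05 | about 3% |
| 6 | 0 | −0.24 | 16% |
| 6 | −0.25 (they improve) | −0.43 | 50% |
| 4 | 0 | −0.16 | 10% |
| 8 | 0 | −0.32 | 26 to 27% |
| 12 | 0 | −0.48 | 54% |

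The result depends on the assumptions. With 12 resolving by 2 SD and no change in the rest, the rate is 96%. With a within-subgroup SD of 0.5, the second row rises from 16% to 38%.

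**The reverse error.** If 6 threat responders do not change and the other 19 improve by 0.75, the mean change is 19 × (−0.75)/25 = −0.57 and the test is significant in about 75% of studies.

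**What the individual-level analyses add.**
- The per-trial counts bear on Objective 2 descriptively. The only threshold defined for them is the 5 ms RMSSD change, so as written they cover HRV.
- The affect reliable-change count names no trial and does not separate worsening from improvement.
- Separate totals per trial do not link people. Five unfavourable responses at Trial 1 and five at Trial 3 could be the same five people or ten different ones.

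**What a paired count can deliver.** If k people resolve and nobody develops new threat, the exact two-sided McNemar p-value is 2 × 0.5^k: 0.25 for 3, 0.063 for 5, 0.031 for 6 and 0.008 for 8. The exact 95% lower limit for the share of changers who resolved is 0.025^(1/k), which is 48% for 5 of 5.

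**Why not simply test the threat subgroup.** If the worst 20% at Trial 1 are selected and nothing truly changes, their apparent improvement is (1 − ρ) × 1.40 SD of the Trial 1 score, where ρ is the between-trial correlation. That is 0.98, 0.70 and 0.42 SD for ρ = 0.3, 0.5 and 0.7. New threat at Trial 3 must therefore be shown beside resolved threat.

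**The case against.** The strongest reply is that the authors foresaw that a mean can hide opposite responses. They added individual-level analyses for that reason, and the last of these is aimed at repeated trials. A reader might infer that test (iii) carries Objective 2 alone, or that Objective 2 goes unanswered. The documents do not support either reading: the per-trial HRV counts address it descriptively.

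A reader might also infer that the protocol predicts a threat minority on the affect scales. It does not. The prediction stands in the HRV item, and Objective 2 names no instrument, so the share showing threat in affect is an assumption. Recruiting highly self-critical people may raise that share.

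The 3% figure needs the other participants to lose benefit, which no document predicts. When the others improve, or about half the sample shows threat, the test does much better. The study is also exploratory, and a table with perhaps six informative people is imprecise.

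All of this stands, and it narrows the point. It does not supply a direction for test (iii), a trial for the affect count, or any link between a person's Trial 1 and Trial 3 responses.

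**Conclusion.** The concern holds in this limited form. Test (iii) is a legitimate average over all participants, but it is a poor answer to a question about those who show threat, and its direction is unstated. The individual-level analyses partly cover the question for HRV. They leave affect without a stated trial or direction, and neither measure is followed within person.

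The size depends on figures that the plan does not give. With 6 of 25 fully resolving by 1 SD, the chance of a significant test (iii) runs from about 3% to 50% according to what the other 19 do. With no change in the rest, it runs from 10% with 4 resolving to 54% with 12. These rates assume a within-subgroup SD of 1, no dropout and two-sided 0.05. They show that full resolution in a minority can come out as no change, not that it will.

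**What to change.** In the Data analysis section, under Objective 2:

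1. Report the planned affect reliable-change classification by direction (worsened, no reliable change, improved) at Trial 1 and at Trial 3. Worsened means a reliable rise in negative affect or a reliable fall in positive affect.
2. Cross-tabulate Trial 1 against Trial 3 within person, with a column for those who have no Trial 3.
3. Give the number whose threat resolved beside the number with new threat, with an exact confidence interval for the paired change.
4. Do the same for the unfavourable HRV responses already counted in each trial.
5. Keep test (iii), described as an average over all participants, and state for each affect scale which direction is favourable.

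The change uses measures already planned. It costs some wording and one more table. The intervals will be wide (five resolvers with no reversals give p = 0.063), so the conclusion will be modest.
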